2.2. Specifications by Methods of Measurements

The same imaging-based method of assessment and the same technique should be used to characterize each identified and reported lesion at baseline and during follow up. CT and MRI are acceptable (see below). Imaging-based evaluation is preferred to evaluation by clinical examination when both methods have been used to assess the anti-tumor effect of a treatment.

¹Therasse P, Arbuck SG, Eisenhauser EA, et al. New guidelines to evaluate the response to

treatment in solid tumors. J Natl Cancer Inst 2000; 92:205-16.

2.2.1. Clinical examination. For lesions that are only evaluable on clinical examination in patients with locally advanced disease, refer to criteria for evaluation in Appendix C.

2.2.2. Chest X-ray. Lesions on chest X-rays are not acceptable as measurable lesions.

2.2.3. CT and MRI. CT and MRI are the best currently available and most reproducible methods for measuring target lesions selected for response assessment. Conventional CT and MRI should be performed with contiguous cuts of 10 mm or less in slice thickness. Spiral CT should be performed by use of a 5-mm contiguous reconstruction algorithm; this specification applies to the tumors of the chest, abdomen, and pelvis, while head and neck tumors and those of the extremities usually require specific protocols. More details concerning the use of these methods of assessment for objective tumor response evaluation are provided in Appendix I.²

2.2.4. Ultrasound. Ultrasound should not be used to measure tumor lesions.

2.2.5. Endoscopy and laparoscopy. These techniques should not be used to measure tumor lesions.

2.2.6. Tumor markers. Tumor markers should not be used to measure tumor lesions.

3. Tumor Response Evaluation

3.1. Baseline Evaluation

3.1.1. Assessment of overall tumor burden and measurable disease. To assess objective response, it is necessary to estimate the overall tumor burden at baseline to which subsequent measurements will be compared. Only patients with measurable disease at baseline should be included in protocols where objective tumor response is the primary endpoint. Measurable disease is defined by the presence of at least one measurable lesion (as defined in Section 2.1). If the measurable disease is restricted to a solitary lesion, its neoplastic nature should be confirmed by cytology/histology.

3.1.2. Baseline documentation of "target" and "nontarget" lesions. All measurable lesions up to a maximum of 5 lesions per organ and 10 lesions in total, representative of all involved organs, should be identified as target lesions and recorded and measured at baseline. Target lesions should be selected on the basis of their size (those with the longest diameter) and their suitability for accurate repeated measurements (either by imaging techniques or clinically). A sum of the longest diameter for all target lesions will be calculated and reported as the baseline sum longest diameter. The baseline sum longest diameter will be used as the reference by which to characterize the objective tumor response.

All other lesions (or sites of disease) should be identified as nontarget lesions and should also be recorded at baseline. Measurements of these lesions are not required, but the presence or absence of each should be noted throughout follow-up.

3.2. Response Criteria

3.2.1. Evaluation of target lesions. This section provides the definitions of the criteria used to determine objective tumor response for target lesions. The criteria have been adapted from the original WHO Handbook, taking into account the measurement of the longest diameter only for all target lesions:

Complete Response—the disappearance of all target lesions; Partial Response at least a 30% decrease in the sum of the longest diameter of target lesions, taking as reference the baseline sum longest diameter; Progressive Disease—at least a 20% increase in the sum of the longest diameter of target lesions, taking as reference the smallest sum longest diameter recorded since the treatment started or the appearance of one or more new lesions; Stable Disease—neither sufficient shrinkage to qualify for partial response nor sufficient increase to qualify for progressive disease, taking as reference the smallest sum longest diameter since the treatment started. If the investigator's assessment of progressive disease is equivocal, and in the investigator's opinion the patient is still deriving benefit from treatment, treatment with CX-4945 should be continued, and the patient should be re-evaluated at the next tumor assessment timepoint.

3.2.2. Evaluation of nontarget lesions. This section provides the definitions of the criteria used to determine the objective tumor response for nontarget lesions: complete response—the disappearance of all nontarget lesions; incomplete response/stable disease—the persistence of one or more nontarget lesion(s); and progressive disease—the appearance of one or more new radiographically identified lesions and/or unequivocal progression of existing nontarget lesions. A new radiographically identified lesion is defined as a lesion that has not previously been seen in prior imaging studies, and that has increased in size to either a diameter larger than the size of the slice thickness being used for that imaging modality or at least 5 mm, whichever is larger.

3.2.3. Evaluation of best overall response. The best overall response is the best response recorded from the start of treatment until disease progression/recurrence (taking as reference for progressive disease the smallest measurements recorded since the treatment started). In general, the patient's best response assignment will depend on the achievement of both measurement and confirmation criteria (see Section 3.5.1). Table 1 provides overall responses for all possible combinations of tumor responses in target and nontarget lesions with or without the appearance of new lesions.

² See Appendix I of the Therasse et al. 2000 article.

| RECIST Best Overall Response: Patients with Measurable Disease | | | | | | | | |
|---|--------------------|-------------|-------------------------|--|--|--|--|--|
| Target Lesions | Non-target Lesions | New Lesions | Overall Response | | | | | |
| CR | CR | No | CR | | | | | |
| CR | SD | No | PR | | | | | |
| PR | Non-PD | No | PR | | | | | |
| SD | Non-PD | No | SD | | | | | |
| PD | Any | Yes or No | PD | | | | | |
| Any | PD | Yes or No | PD | | | | | |
| Any | Any | Yes | PD | | | | | |

Table 1. Overall responses for all possible combinations of tumor responses in target and nontarget lesions with or without the appearance of new lesions

CR = complete response; PR = partial response; SD = stable disease; and PD = progressive disease. See text for more details.

Note: If the investigator's assessment of progressive disease is equivocal, and in the investigator's opinion the patient is still deriving benefit from treatment, treatment with CX-4945 should be continued, and the patient should be re-evaluated at the next tumor assessment timepoint.

- Patients with a global deterioration of health status requiring discontinuation of treatment without objective evidence of disease progression at that time should be classified as having "symptomatic deterioration." Every effort should be made to document the objective disease progression, even after discontinuation of treatment.
- In some circumstances, it may be difficult to distinguish residual disease from normal tissue. When the evaluation of complete response depends on this determination, it is recommended that the residual lesion be investigated (fine-needle aspiration/biopsy) before confirming the complete response status.

3.2.4. Frequency of tumor re-evaluation. Frequency of tumor re-evaluation while on treatment is defined in this study as every 8 weeks.

3.3. Confirmatory Measurement/Duration of Response

3.3.1. Confirmation. The main goal of confirmation of objective response in clinical trials is to avoid overestimating the response rate observed. This aspect of response evaluation is particularly important in nonrandomized trials where response is the primary endpoint. In this setting, to be assigned a status of partial response or complete response, changes in tumor measurements must be confirmed by repeat assessments that should be performed no less than 4 weeks after the criteria for response are first met.

In the case of stable disease, measurements must have met the stable disease criteria at least once after study entry at a minimum interval of 8 weeks.

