10.2.2. Registration Procedures

Prior to registration and any study-specific evaluations being performed, all patients must have given written informed consent for the study and must have completed the pre-study evaluations.

Upon signing the informed consent, the patient will be given a screening number. Once the patient has been confirmed eligible to be enrolled in the study, a patient identification number will be assigned via the Medidata RAVE[®] (refer to the eCRF completion guidelines for specific instructions) that will be used on all documentation for the subject throughout the study. Patient identification numbers will be assigned in ascending order, and numbers will not be omitted or reused. Investigator will verify that patients are eligible per the protocol specific Inclusion and Exclusion criteria. No patient is allowed to begin study treatment prior to registration and assignment of a patient identification number. The maximum allowable time between registration and the first administration of study treatment is 7 calendar days.

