11.7. PREMEDICATION

11.8. VITAMIN D SUPPLEMENT

12. STUDY ASSESSMENTS

12.1. DEFINITION OF STUDY ASSESSMENTS

The study period will begin on Day 1, and patients will be followed until disease progression, death, or withdrawal of consent from the study.

Screening tests and evaluations will be used to determine the eligibility of each patient for study inclusion. All patients must provide written informed consent before any study-specific procedures and assessments are performed and any exclusionary medications are discontinued for the purposes of establishing eligibility. Screening evaluations will be performed within the 14 days preceding Day 1, unless otherwise specified (for list of study assessments, see the study flowchart in Appendix A). Results of tests or examinations performed as standard of care prior to obtaining informed consent prior to study entry may be used rather than repeating required tests.

a. Physical Examination

The initial complete physical examination should include the evaluation of the head, eyes, ears, nose, and throat (HEENT); cardiovascular, dermatological, musculoskeletal, respiratory, gastrointestinal, and neurological systems. Height and weight will also be recorded. Subsequent limited physical examinations for assessment of toxicity may be restricted to evaluation of specific systems or areas of interest, including those with previously abnormal findings or associated with symptomatic or laboratory evidence of toxicity. Changes from baseline abnormalities should be recorded at each subsequent physical examination. New or worsened abnormalities should be recorded as adverse events if appropriate.

b. Vital Signs

Vital signs will include measurements of pulse, systolic and diastolic blood pressure while the patient is in a seated position, respiratory rate, and temperature. Vital signs will be recorded at screening and at regular intervals throughout the study, including at the end of the study or early termination, as appropriate.

c. Electrocardiographic Assessment

Twelve-lead electrocardiograms (ECGs) are required at screening.

d. Vitamin D level Assessment

Measurement of serum 25-hydroxyvitamin D (25[OH]D or calcidiol) is required at screening. Follow-up 25(OH)D measurements will be performed every three months.

e. Tumor and Response Assessments

Baseline Assessments

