12.3. ASSESSMENTS DURING TREATMENT

All visits must occur within ± 3 days from the scheduled date, unless otherwise noted. All assessments will be performed on the day of the specified visit unless a time window is specified. Assessments scheduled on the day of study drug administration (Day 1) of each cycle should be performed prior to study drug administration, unless otherwise noted.

Please see the Study Flowchart provided in Appendix A for the schedule of treatment period assessments.

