APPENDIX A

STUDY FLOWCHART

| | Screening | | | | Tre | atment | | | | 3 month follow-up (only |
|--|-------------------|----------|-------------------------------------|-------------------------------------|---------------------------|-------------------------------------|---|----------------------------|--|--|
| Assessment or Procedure | Days -14 to -1 | Day 1 | Every 4 Weeks (±3 Days) | Every 8 Weeks (±3 Days) | Week 8 (±3 Days) | Every Week 12 (±3 Days) | Clinical Response if before Wk 24 | Week 24 (±3 Days) | 4 weeks after completion of protocol therapy | required for pts without confirmed PD and ongoing toxicities ") |
| Informed Consent ^a | X | | | | | | | | | |
| Inclusion/Exclusion | X | | | | | | | | | |
| Medical, surgical, and cancer history, and demographics | X | | | | | | | | | |
| Complete physical examination ^b | X | | | | | | | | | |
| Limited physical examination | | | X | | | | | | X | |
| Weight and Vital Signs ^c | X | X | X | | | | | | X | |
| ECOG Performance Status (Appendix I) | X | x | X | | | | | | X | |
| 12-Lead Electrocardiogram | X | | | | | | | | | |
| Tumor Assessments ^d | X | | | X | | | | | X | X ^{r,s} |
| Digital photographs ^e | X | | | X | | | | | X | |
| Tumor biopsy ^f | X | | | | Xf | | Xf | Xf | Xf | |
| Hematology ^g | X | | X | | | | | | Xq | Xq |
| Serum Chemistry ^h | X | | X | | | | | | Xq | Xq |
| Urinalysis ⁱ | X | | | | | | | | | |
| Serum vitamin D level ^j | X | | | | | X | | | | |
| Serum or urine pregnancy test ^k | X | X | X | | | | | | X | |
| CX-4945 accountability ¹ | | | X | | | | | | X | |
| Dispense CX-4945 ¹ | | X | X | | | | | | | |
| Concomitant medications ^m | X | X | X | | | | | | X | |
| Evaluation of Adverse Events | X ⁿ | x | X | | | | | | X | X ⁿ |
| Cancer-related medical or surgical procedures ° | | x | X | | | | | | X | |
| Dispense antiemetics and loperamide ^p (IMODIUM®) | | X | X | | | | | | | |

BCC = basal cell carcinoma

Note: Results of tests or examinations performed as standard of care prior to obtaining informed consent and within 14 days prior to study entry may be used rather than repeating required tests.

- a. All patients must provide written informed consent prior to any study-specific procedure being performed and any exclusionary medications are discontinued for the purposes of establishing eligibility. Patients will sign two informed consent forms: one for study participation, and a separate consent detailing teratogenic risk.

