9. INTERIM ANALYSIS

No interim analysis is planned for this study.

10.DATA CONVENTIONS FOR ANALYSIS

10.1General Statistical Principles

All statistical processing will be performed using SAS® unless otherwise stated. Any statistical tests will be two-tailed at significance level of 0.05 unless otherwise specified.

All observed and derived variables (e.g., change from baseline, percentage change from baseline, and response status) used in the summaries of analyses will be presented in by-subject listings. Unless otherwise noted, the data will be sorted first by treatment assignment, then by subject number and then by date within subject number.

Efficacy and safety results will be summarized descriptively. Categorical parameters will be summarized by the number and percentage of subjects in each category. Denominators for percentages will be appropriate to the purpose of the analysis. Percentages will typically be presented to one decimal (Note: 0% and 100% will be in integer format). Continuous parameters will be summarized as number of subjects, mean, standard deviation (SD), median, minimum, and maximum.

10.2Study Day

Day 1 is defined as the date of first study drug administration. Study day is calculated relative to the date of Day 1. For subjects who did not have a recorded date of first study drug administration, study day will not be calculated.

10.3Baseline and Change from Baseline

Baseline is defined as the last non-missing assessment prior to the first administration of study drug. Change from baseline is defined as post-baseline value minus baseline value unless otherwise specified. Percent change from baseline is (Change from baseline / Baseline) * 100%.

10.4Analysis Visit Window

Results will be summarized according to the visit as recorded in the eCRF. No visit windows will be applied.

10.5Multiple Comparisons

Not applicable. There will be no formal hypothesis testing.

11.STATISTICAL EVALUATION

11.1Subject Disposition

The number and percentage of subjects screened, enrolled, included in key analysis populations, completing the study, and withdrawing from the study (together with the reasons for withdrawal) will be summarized using frequencies and percentages, overall and by cohort (treatment-duration-increment, expansion).

A by-subject listing will show all subjects enrolled and their disposition.

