- Patients who started a new anti-cancer therapy prior to documented PD or death will be censored at the last tumor assessment prior to initiation of new anti-cancer therapy.
- **Rate of patients with CR+PR+SD (regardless of duration):** Defined as the percentage of patients who have achieved CR, PR, or SD.
- **Duration of CR+PR+SD:** Defined as the time from the date of first documented response (CR or PR) or Stable Disease (SD) until the date of progressive disease or death from any cause, whichever occurs first, for patients with CR, PR or SD. The duration will be censored as follows:
 - Patients who had no event (i.e., they did not die or have PD) will be censored at the date of their last tumor assessment.
 - Patients who started a new anti-cancer therapy prior to documented PD or death will be censored at the last tumor assessment prior to initiation of new anti-cancer therapy.

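### The 8-week minimum for RECIST stable disease makes no allowance for the ±3-day scan window, so an on-schedule first scan can be too early to establish SD as best overall response

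*Protocol*

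**What the plan says.** - **SD rule.** Under Protocol Appendix B 3.3.1, for SD, "measurements must have met the stable disease criteria at least once after study entry at a minimum interval of 8 weeks". Appendix B 3.2.3 makes the best response depend on confirmation as well as on measurement. SAP 11.9.1 takes Best Overall Response from the protocol appendices.
- **Scan schedule.** Appendix B 3.2.4: "Frequency of tumor re-evaluation while on treatment is defined in this study as every 8 weeks". Protocol 12.3: "All visits must occur within ± 3 days from the scheduled date, unless otherwise noted". The tumor-assessment column of the Appendix A flowchart carries the same ±3 days.
- **Clock.** SAP 10.2: "Day 1 is defined as the date of first study drug administration". Protocol 12.1: "The study period will begin on Day 1, and patients will be followed until disease progression, death, or withdrawal of consent from the study". Protocol 10.2.2: "The maximum allowable time between registration and the first administration of study treatment is 7 calendar days". Neither document defines *study entry*, the term on which the SD interval hangs.
- **Neighbouring rules.** Appendix C, for locally advanced disease, gives SD no minimum. In SAP 11.9.2 the disease control rate (DCR) counts SD only if it lasts at least 6 months. A separate CR+PR+SD rate, whose title waives any duration requirement, is "Defined as the percentage of patients who have achieved CR, PR, or SD".

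**The concern.** The SD minimum equals the nominal scan interval exactly, yet the protocol permits the scan to be early. A site can therefore follow the schedule and still obtain an SD that fails the rule by 1 to 3 days. If the next scan shows progression, or there is none, no qualifying SD exists. SAP 11.9.1 offers PD and NE as categories but does not say which applies in this case. The reported RECIST best overall response would then turn on the calendar day of a compliant scan, and on how the programmer reads *study entry*. The metastatic group is very small (SAP 6 records 2 expansion patients), so one such patient would be visible in the table.

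**Working it through.** The plan makes no calculation on this point, so there is no figure to reproduce. The check is a day count.

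**Inputs**
- SD minimum: 8 weeks = 8 × 7 = 56 days (Appendix B 3.3.1).
- First on-treatment scan: Week 8, shifted by d = −3 to +3 days (Appendix B 3.2.4, Protocol 12.3, Appendix A).
- Day 1 = first dose (SAP 10.2).
- Registration: r = 0 to 7 days before first dose (Protocol 10.2.2).
- Baseline imaging: Day −14 to Day −1 (Protocol 12.1).

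One step is an inference. Appendix B 3.2.3 cites a Section 3.5.1 for the confirmation criteria, and the appendix as given has no such section. I take 3.3.1, its only confirmation text, as the target.

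**Step 1: anchor at Day 1.** Days from first dose to scan = nominal offset + d.
- Week 8 = Day 57 (offset 56): 53, 54, 55, 56, 57, 58, 59. Below 56: 3 of 7.
- Week 8 = Day 56 (offset 55): 52, 53, 54, 55, 56, 57, 58. Below 56: 4 of 7.

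**Step 2: other anchors.** The earliest compliant scan must satisfy 53 + r ≥ 56 (or 52 + r ≥ 56 under the Day 56 convention).

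| Anchor | Window days short, Week 8 = Day 57 | Window days short, Week 8 = Day 56 |
|---|---|---|
| Registration on Day 1 (r = 0) | 3 of 7 | 4 of 7 |
| Registration 1 day before | 2 of 7 | 3 of 7 |
| Registration 2 days before | 1 of 7 | 2 of 7 |
| Registration 3 days before | 0 | 1 of 7 |
| Registration 4 to 7 days before | 0 | 0 |
| Baseline scan Day −1 | 2 of 7 | 3 of 7 |
| Baseline scan Day −2 | 1 of 7 | 2 of 7 |
| Baseline scan Day −3 | 0 | 1 of 7 |
| Baseline scan Day −4 or earlier | 0 | 0 |

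**Step 3: does a later scan repair it?** The earliest compliant Week 16 scan is 112 − 3 = 109 days after first dose, well past 56. The rule asks for SD only once, so SD at Week 16 satisfies it.

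**Step 4: which endpoints use the rule?**
- RECIST best overall response: yes.
- ORR and CRR count only CR and PR; PFS counts progression and death. None uses the SD minimum.
- DCR: a patient with SD for 6 months on 8-weekly scans has SD at Week 16, so Step 3 applies.
- CR+PR+SD rate: on its plain wording an SD at 53 days counts.

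**Step 5: size of one reclassification.** One patient moves the share of metastatic patients with SD as best response by 100/n points. The Efficacy population holds 2 metastatic expansion patients plus an unstated number from the run-in. Assuming 0 to 6 of those, n runs from 2 to 8: 100/2 = 50 points down to 100/8 = 12.5 points.

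**Step 6: after the fix.** With a minimum of 56 − 3 = 53 days from first dose and Week 8 = Day 57, 0 of 7 window days fail. Under the Day 56 convention the earliest scan is at 52 days and 1 of 7 would still fail, so the fix must name the convention.

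**The case against.** The strongest objection is that the anchor decides everything. Protocol 10.1.1 and 10.1.2 use *study entry* in the sense of enrolment, which can support registration as the starting point; with registration at least 3 days before Day 1 there is no shortfall (Day 57 convention). This stands as a condition on the finding. Usage elsewhere leans towards Day 1: Protocol 12.2 and Appendix A apply one 14-day span to the period before Day 1 and to the period before study entry, and Protocol 12.1 starts the study period on Day 1. A classification that turns on an undefined term needs settling either way.

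SAP 10.4, which applies no visit windows, might seem to dispose of the matter. It governs summaries by visit and does not relax a minimum interval in the response criteria.

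Several stronger readings are tempting, and the documents do not support them.
- *The disease control rate is distorted.* DCR requires SD of at least 6 months, so such a patient has later qualifying scans. It could change only if an early SD were also refused as the first documented SD, which would restart the clock at Week 16. For progression at Week 40 that gives (280 − 112)/30.4375 = 5.5 months instead of (280 − 53)/30.4375 = 7.5. No text says to do this.
- *The CR+PR+SD rate loses patients.* Its title waives duration. The loss arises only if the Appendix B minimum is imported, and nothing directs that.
- *About 43% of first SDs are lost.* The ratio 3/7 = 43% is a share of window days. As a share of scans it needs uniform timing, and a loss also needs SD on that scan and then progression or no scan. The documents do not allow that joint probability to be estimated.
- *The SD rules conflict across cohorts.* Separate criteria for metastatic and locally advanced disease are deliberate (Protocol 9.2, SAP 11.9.1).

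**Conclusion.** The point holds in a narrow form and is minor. With the interval anchored at Day 1 and Week 8 at Day 57, compliant first scans at 53, 54 or 55 days cannot establish RECIST SD. A patient whose only SD is on such a scan loses it as best overall response. The effect falls mainly on metastatic patients; in locally advanced disease it can reach at most the RECIST component of the composite. One affected patient would move the metastatic SD share by 12.5 to 50 points under the denominator range assumed above, but the documents do not show that any patient is affected.

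The conclusion rests on three things: the Day 1 anchor, which the text favours without stating; the reading of Appendix B 3.3.1 as the confirmation rule behind best overall response; and the absence of SD at Week 16. The RP2D, which is the primary endpoint, does not use the rule.

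**What to change.** In Protocol Appendix B 3.3.1 and SAP 11.9.1:
- state that the SD interval runs from Day 1 (first dose) and that Week 8 is nominally Day 57;
- set the SD minimum at 8 weeks less the 3-day visit window, that is 53 days after first dose.

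In SAP 11.9.2, state that the CR+PR+SD rate carries no minimum, as its title implies. Do not add a minimum to Appendix C, which would be a new restriction on locally advanced SD and is not needed to close this gap.

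The cost is a few sentences, no new data, and an SD minimum 3 days shorter. The trial is open-label and the SAP already records early termination of metastatic enrolment, so the rule should be set without reference to individual outcomes and recorded as a clarification in SAP 12.
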